6. TRIAL OBJECTIVES AND ENDPOINTS

6.1. Trial Objectives

6.1.1. Induction Period Primary Objective

To assess endoscopic improvement following treatment with RPC1063

6.1.2. Induction Period Secondary Objectives

- To characterize clinical improvement, response, and remission following treatment with RPC1063
- To assess changes in intestinal and blood biomarkers following treatment with RPC1063 by characterizing the following:
 - Intestinal mucosa histopathologic disease activity
 - Select cellular, protein, and molecular biomarkers in the intestinal mucosa and blood
- To assess the pharmacokinetics (PK) and pharmacodynamics (PD) of RPC1063
- To assess the safety of RPC1063

6.1.3. Extension Period Primary Objective

To characterize the longer term safety of continued dosing of RPC1063

6.1.4. Extension Period Secondary Objectives

- To characterize endoscopic improvement at Week 52
- To characterize the histopathological changes of the intestinal mucosa at Week 52
- To characterize the effect of RPC1063 in maintaining clinical improvement over time

6.2. Endpoints

6.2.1. Induction Period Endpoints

Patients in the Induction Period will be assessed for the following efficacy endpoints:

Primary Efficacy Endpoint

- Change in SES-CD score from baseline at Week 12.

Other Efficacy Endpoints

- Change in CDAI score from baseline at Week 12
- Proportion of patients with clinical remission based on CDAI at Week 12
- Proportion of patients with clinical response based on CDAI at Week 12
- Proportion of patients with clinical remission based on PRO2 definitions at Week 12

- Proportion of patients with clinical response based on PRO2 definitions at Week 12
- Proportion of patients with endoscopic remission based on SES-CD definitions at Week 12
- Proportion of patients with endoscopic response based on SES-CD definitions at Week 12
- Change in intestinal mucosa histopathologic features and disease activity
- [REDACTED]
- [REDACTED]
- [REDACTED]
- [REDACTED]
- [REDACTED]
- [REDACTED]
- Improvement in perianal and enterocutaneous fistulas at Week 12 in those patients with fistulas at baseline

6.2.2. Extension Period Efficacy Endpoints

Patients in the Extension Period will be examined for the following efficacy endpoints:

- Proportion of patients in endoscopic remission based on SES-CD definitions at Week 52
- Proportion of patients in endoscopic response based on SES-CD definitions at Week 52
- Proportion of patients in clinical remission based on CDAI at Week 52
- Proportion of patients in clinical response based on CDAI at Week 52
- Proportion of patients in clinical remission based on PRO2 definitions at Week 52
- Proportion of patients in clinical response based on PRO2 definitions at Week 52
- Proportion of patients in clinical remission at Week 52 based on CDAI and PRO2 definitions who are off corticosteroids of those on corticosteroids at baseline
- Proportion of patients in clinical remission based on CDAI over time
- Proportion of patients in clinical response based on CDAI over time
- Proportion of patients in clinical remission based on PRO2 definitions over time
- Proportion of patients in clinical response based on PRO2 definitions over time

- Change in intestinal mucosa histopathologic features, histologic disease activity, and biomarkers over time
- Change in fecal calprotectin and serum C-reactive Protein levels over time
- Improvement in perianal and enterocutaneous fistulas in those patients with fistulas at baseline over time

6.2.3. Safety Endpoints

The incidence, severity, relationship and type of TEAEs, SAEs, AEs leading to discontinuation of investigational drug, and AEs of special interest, and clinically meaningful changes from baseline on clinical laboratory measures, vital signs, electrocardiograms (ECGs), and physical examination will be assessed.

Safety assessments will include the following:

- Collection of AEs
- Physical examinations
- Vital sign measurements
- ECG results
- Optical coherence tomography
- Pulmonary function tests (PFTs) (FEV₁, FVC, and diffusion capacity of the lung for carbon monoxide [DLCO], where available)
- Clinical laboratory tests

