10.3. Vital Sign Measurements

The following vital signs measurements will be collected for Day 1 (Baseline, Hour 1, Hour 2, Hour 3, Hour 4, Hour 5, and Hour 6, Week 4, Week 8, Week 12, Week 24, Week 36, Week 48, Week 52, and all visits subsequent to Week 52 according to the Protocol-defined schedule of vital signs assessments:

- Heart Rate (sitting; 'HR')
- Systolic Blood Pressure (sitting; 'SBP')
- Diastolic Blood Pressure (sitting; 'DBP')

The baseline value for a given patient in any tabulation or listing will be the lowest pre-dose value observed on Day 1.

Two separate continuous tabulations will be generated: for Study Day 1, actual values and change from baseline will be summarized continuously for Baseline, Hour 1, Hour 2, Hour 3, Hour 4, Hour 5, Hour 6, and Hour 7. Separately, for the post-baseline visits, the actual values and change from baseline will be summarized continuously for Week 4, Week 8, Week 12, Week 24, Week 36, Week 48, Week 52, and all visits subsequent to Week 52 according to the Protocol-defined schedule of vital signs assessments.

For Study Day 1, Heart Rate will be summarized categorically for the following categories for Day 1 for Hours 1, 2, 3, 4, 5, 6, and Minimum Overall:

- ≥ 65
- 60-64
- 55-59
- 50-54
- 45-49
- 40-44
- 35-39
- < 35

The proportion of patients requiring extended cardiac monitoring beyond Day 1, Hour 6, based on the criteria in Section 12.1.9. Guidelines for Monitoring Patients Taking Their First Dose of RPC1063 in the protocol, will be summarized categorically and will also be presented in a listing showing the criteria triggering a subject to be included in the listing. A listing of vital signs for the subjects who required extended cardiac monitoring per protocol criteria will be presented.

The number and percentage of patients who meet the criteria for clinically relevant abnormalities for HR, SBP, and DBP will be summarized by visit. The criteria for clinically relevant abnormalities are shown in the following table. All increases and decreases are relative to pre-dose on Day 1.

Table 7. Vital Sign Abnormality Cutoffs

Vital Sign	Criteria for Abnormalities
HR	> 120 bpm < 45 bpm
SBP	> 180 mmHg < 90 mmHg
DBP	> 105 mmHg < 50 mmHg

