10.4. Electrocardiogram

The following ECG values will be included for summarization:

- QTcB – Bazett’s Correction
- QTcF – Fridericia’s Correction
- PR Duration
- QRS Duration
- QT Duration
- RR Duration
- Ventricular Rate

QTcF is the primary measure of corrected QT, with Bazett’s correction serving as a supportive measure. For all ECG measurements, actual values and change from baseline will be summarized continuously by visit.

The proportion of patients with ECG outliers will be presented overall and by visit. For this analysis, the categories defined below will be used:

- QT > 480 milliseconds (ms), QT > 500 ms, Female: QTcF > 470 ms, and Male: QTcF > 450 ms
- PR < 120 ms, PR > 200 ms

The interpretation of ECG results will be presented by visit (‘Normal’, ‘Abnormal, not clinically significant’, ‘Abnormal, clinically significant’).

ECG abnormalities upon first dose of study drug will be summarized categorically, with the types of abnormalities sorted alphabetically within each time point.

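### SAP Table 7 holds only absolute vital-sign limits, so the incidence table cannot count patients with a meaningful change from baseline and counts blood pressures already beyond a limit before dosing

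*Protocol*

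**What the plan says.** **Endpoint.** Protocol 6.2.3 states that "clinically meaningful changes from baseline on clinical laboratory measures, vital signs, electrocardiograms (ECGs), and physical examination will be assessed". SAP 4.2.4 carries the same endpoint. Neither document says how large a vital-sign change must be to qualify.

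**Incidence table.** SAP 10.3 plans this tabulation: "The number and percentage of patients who meet the criteria for clinically relevant abnormalities for HR, SBP, and DBP will be summarized by visit". It then adds: "All increases and decreases are relative to pre-dose on Day 1". Table 7 follows with three rows:

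- HR: "> 120 bpm < 45 bpm"
- SBP: "> 180 mmHg < 90 mmHg"
- DBP: "> 105 mmHg < 50 mmHg"

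No row is an increase or a decrease, and no row requires the patient to have been within the limit before dosing.

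**Baseline.** SAP 10.3 fixes it for vital signs: "The baseline value for a given patient in any tabulation or listing will be the lowest pre-dose value observed on Day 1". Protocol 12.1.9 calls for three sets of readings before the first dose and a single reading at each hour afterwards.

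**Other planned vital-sign summaries.** SAP 10.3 also summarises actual values and change from baseline continuously, by hour on Day 1 and by visit afterwards. It tabulates Day 1 heart rate in bands and reports the proportion of patients needing extended cardiac monitoring. SAP 5 includes the minimum and maximum in continuous summaries and lists safety data by patient.

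**The concern.** The endpoint concerns change, and the sentence leading into Table 7 speaks of increases and decreases, but the table contains only levels. That sentence has nothing to act on, and the endpoint has no patient count for vital signs.

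This matters for three reasons. Protocol 9.2 justifies the dose escalation by a lower chance of a clinically meaningful drop in heart rate or blood pressure, and no planned table counts patients with such a drop. Safety is the primary objective of the Extension Period. The trial also has no control arm, so comparison with the patient's own baseline is the main way to separate what arose on treatment from what was there before. If change cut-offs are not fixed in the SAP, they may be chosen during programming or after the data have been seen.

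**Working it through.** The documents give no figure to reproduce here. The check compares the text and then does simple arithmetic on the Table 7 limits.

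**1. Endpoint against table.** The endpoint needs a baseline-relative criterion, and SAP 10.3 names the reference point for one. Table 7 has six limits (two for each of HR, SBP and DBP), all absolute. Baseline-relative criteria in the table: 0 of 6. By contrast, SAP 10.5 defines a pulmonary function abnormality by two conditions together, below 70% of predicted and below 80% of baseline, so this SAP already uses a baseline-relative rule elsewhere.

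**2. Falls that Table 7 does not count.** The lower limits are strict, so a patient who falls exactly to the limit is not counted. Largest uncounted fall = baseline − lower limit. The baselines below are chosen for illustration.

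| Measure | Baseline | Lower limit | Largest uncounted fall |
|---|---|---|---|
| HR (bpm) | 70 | 45 | 25 (36%) |
| HR (bpm) | 90 | 45 | 45 (50%) |
| SBP (mmHg) | 120 | 90 | 30 (25%) |
| SBP (mmHg) | 140 | 90 | 50 (36%) |
| DBP (mmHg) | 80 | 50 | 30 (38%) |

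**3. Values counted with no change.** SBP of 89 mmHg before dosing and 89 mmHg on drug has a change of 0, yet it is below 90 and counts. The same holds for DBP of 49 and 49 mmHg. The exclusion criteria set no numeric blood-pressure limit. SAP Table 4 has 16 on-treatment visits after baseline (Weeks 4 to 160), so one such patient can be counted up to 16 times. With 60 patients as denominator, each count is 1/60 = 1.7%.

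**4. The same test for low heart rate.** HR below 55 bpm at Screening is an exclusion (Protocol 8.2), and Protocol 12.2.7 has the dose withheld at a pre-dose pulse below 55 bpm. From a pre-dose value of at least 55, a reading below 45 needs a fall of more than 55 − 45 = 10 bpm. A count below 45 bpm therefore does reflect a fall.

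**5. Illustration on assumed values.** The documents give no blood-pressure distribution. Assume pre-dose and on-drug SBP are jointly normal with the same mean of 110 to 120 mmHg, SD 12 to 15, within-patient correlation 0.5 to 0.7 and no drug effect. Take 20 mmHg purely as an example of a change. Simulation with 1,000,000 draws per setting gives:

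- 10% to 46% of patients counted as SBP below 90 were already below 90 before dosing.
- 1.6% to 9.1% of patients show a fall of at least 20 mmHg from ordinary variability alone. In 60 patients that is 60 × 0.016 = 1.0 to 60 × 0.091 = 5.5.
- 69% to 95% of those falls are not counted by the limit of 90.

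The ranges are wide and depend on the assumptions. They show that level and change criteria pick out different patients; they do not predict this trial's results.

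**The case against.** The strongest reply is that the SAP already does what Protocol 13.5 asks: change from baseline is summarised, and abnormal vital signs and outlying ECGs are tabulated. Nothing there promises a count above a change threshold, and the study is descriptive with no hypothesis tests. Much of this stands, and it rules out four stronger readings that a reader might infer.

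- **That large falls are hidden.** They are not. The continuous summaries show the largest fall as the minimum change, and data are listed by patient. Falls go uncounted only in the Table 7 tabulation.
- **That Table 7 is the only patient-level vital-sign rate.** SAP 10.3 also tabulates Day 1 heart-rate bands and extended-monitoring counts. A heart rate that falls from 85 to 46 bpm on Day 1 would appear in the 45–49 band. These are Day 1 summaries, however, and neither counts patients by size of change from baseline.
- **That pre-existing low heart rates inflate the counts.** The rules at 55 bpm in practice prevent this.
- **That SAP 10.4 has the same contradiction.** Its outlier categories, "QT > 480 milliseconds (ms), QT > 500 ms, Female: QTcF > 470 ms, and Male: QTcF > 450 ms" and the PR limits, are absolute too, but that section announces no increases or decreases. Rows for QTcF change would be an optional addition.

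It is also fair to say that change counts would have weaknesses of their own. Baseline is the lowest pre-dose reading, so decreases will tend to be understated and increases overstated, and without a control arm the counts include ordinary variability. That calls for a footnote and careful reading. It does not supply the missing criterion.

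**Conclusion.** The point holds for SAP 10.3 and Table 7. The sentence about increases and decreases has no criterion to apply to, the vital-sign part of the change-from-baseline endpoint has no patient count, and SBP or DBP already beyond a limit before dosing is counted at each visit where it stays there. This follows from the text and rests on no distributional assumption. It does assume that the three rows of Table 7 are complete as read; nothing suggests that text was lost.

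The size is modest. What is missing is the number of patients with a meaningful change; evidence that such changes occurred would still be reported. How many patients are affected cannot be stated, because the documents give neither a vital-sign distribution nor a threshold for a meaningful change. A claim that the plan misses most clinically important changes is therefore unsupported. This is an inexpensive improvement to a descriptive safety table, and no efficacy result depends on it.

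**What to change.** In SAP 10.3 and Table 7:

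1. Keep the absolute rows.
2. For HR, SBP and DBP, add the number and percentage of patients with a prespecified increase or decrease from pre-dose Day 1. The sponsor should set the cut-offs, as reporting thresholds only.
3. For each absolute limit, add the number of patients beyond it who were within it at baseline.
4. Add a footnote saying that baseline is the lowest pre-dose value, so decreases tend to be understated and increases overstated, and that the counts include ordinary variability because there is no control arm.

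If the sponsor prefers not to add change rows, the least that is needed is to remove the sentence on increases and decreases and state how the change-from-baseline endpoint will be assessed for vital signs.

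The cost is SAP wording and a few extra rows in planned tables, using data already collected. Categorical QTcF-change rows in SAP 10.4 may be added but are not needed to resolve this point.

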6.2.4. Pharmacokinetic and Pharmacodynamic Endpoints

Pharmacokinetic and PD endpoints will include the following:

- [REDACTED]
- [REDACTED]
- [REDACTED]

7. INVESTIGATIONAL PLAN

7.1. Overall Trial Design

This Phase 2, multi-center, open-label trial, to be conducted in North America and Europe, is designed to assess the endoscopic improvement, clinical response/remission, and changes in intestinal and blood biomarkers in patients with moderately to severely active Crohn's disease receiving RPC1063 as induction therapy. The trial comprises 2 periods: Induction (12 weeks) and Extension (148 weeks). Patients will be entered into the trial through the Induction Period. A central reader will calculate the SES-CD for eligibility and assessment of the primary endpoint to ensure objectivity.

The safety of patients will be monitored by collection of treatment-emergent AEs, serious adverse events (SAEs), physical examinations, vital sign measurements, ECG results, optical coherence tomography (OCT), pulmonary function tests (PFTs), and clinical laboratory tests.

Patients who discontinue from treatment due to lack of response, AEs, or other reasons, even if alternative treatment is given, will complete an Early Termination Visit and will be followed for 90 days for collection of safety data and for the assessment of their disease status.

7.1.1. Induction Period

The trial will enroll approximately 60 patients with moderately to severely active Crohn's disease. Patient eligibility will be determined during a 5-week Screening Period. All patients who meet eligibility criteria and enter into the trial will complete a 7-day dose escalation regimen consisting of 4 days of treatment with RPC1063/ozanimod HCl 0.25 mg (equivalent to ozanimod 0.23 mg) daily followed by 3 days treatment with RPC1063/ozanimod HCl 0.5 mg (equivalent to ozanimod 0.46 mg) daily (administered as two 0.25 mg capsules), with the final dose level of RPC1063/ozanimod HCl 1 mg (equivalent to ozanimod 0.92 mg) daily dose to be reached on Day 8. Patients will then continue on RPC1063 1 mg daily during the Induction Period for 11 weeks. At Week 12 patients will be evaluated for endoscopic and clinical response/remission.

Patients who complete the Induction Period will have the opportunity to receive continued treatment with RPC1063 in the Extension Period. Investigators should assess patient's clinical status at the end of the Induction Period and, using clinical judgment, determine if the patient should continue into the Extension Period or withdraw from the trial and receive alternative therapy.

Induction Period visit schedule and procedures, including early termination and safety follow-up, are provided in [Table 2](#).

7.1.2. Extension Period

All patients will receive RPC1063 1 mg daily dose in the Extension Period and may receive treatment through Week 160. During the Extension Period, the investigator should continue to assess the patients clinical status and based on clinical judgment determine if the patient should continue or withdraw from the trial and receive alternative therapy. Extension Period visit schedule and procedures, including early termination and safety follow-up, are provided in [Table 3](#).

Patients who complete the Week 160 visit may have the option to immediately enter (without completing the 30-day or 90-day Safety Follow-up Visits) the open-label extension Phase 3 CD Study [REDACTED].

7.2. Criteria for Trial Termination

The Sponsor has the right to terminate the trial prematurely for safety reasons. In addition, the Sponsor may terminate the trial prematurely for administrative reasons. In all cases, all necessary measures must be taken to guarantee appropriate safety follow-up of all patients already included in the trial.

The IEC or IRB and the Regulatory Authorities will be informed in writing about any premature termination of the trial.

7.3. Schedule of Events

The visit schedule and procedures for the Induction Period and Extension Period are provided in [Table 2](#) and [Table 3](#), respectively.

Table 2: Schedule of Events for Induction Period

| | Trial Procedures | Screening Day-35 to 0 | Induction Period | | | | Early Term Visit | Safety Follow-up | |
|---|---------------------|-----------------------------|----------------------|---------------------|---------------------|------------------------|---------------------|--------------------------|---|
| | | | Dose Escalation | 1 mg Dose | | | | Last Dose +30 ±3 days | Last Dose +90 ±10 days ^f |
| | | | Visit I1 | Visit I2 | Visit I3 | Visit I4 | | | |
| | | | Day 1 ^{a,b} | Week 4 ^b | Week 8 ^b | Week 12 ^{b,c} | | | |
| | | | Day 1 | Day 28±3 | Day 56±3 | Day 84±3 | | | |
| Informed consent | X | | | | | | | | |
| Inclusion/exclusion criteria | X | X | | | | | | | |
| Demographics | X | | | | | | | | |
| Medical history ^{d,e} | X | X | | | | | | | |
| Viral serology ^f | X | | | | | | | | |
| Stool culture ^g | X | | | | | | | | |
| Dispense investigational drug | | X | X | X | X | | | | |
| Administer investigational drug at clinic | | X | X | X | X | | | | |
| Review drug compliance | | | X | X | X | X | | | |
| Prior and concomitant medications | X | X | X | X | X | X | X | X | |
| Medical procedures (non-trial) | | X | X | X | X | X | X | | |
| Efficacy Assessments | CDAI patient diary | X ^h | X | X | X | X | X | | |
| | CDAI clinical score | X ^h | X | X | X | X | X | | |
| | Colonoscopy | X ^h | | | | X ⁱ | X ^j | | |
| | SES-CD | X ^h | | | | X | X | | |
| | Colonic biopsy | X | | | | X | X ^j | | |

| | Trial Procedures | Screening Day-35 to 0 | Induction Period | | | | Early Term Visit | Safety Follow-up | |
|------------------------------|--|--------------------------|----------------------|---------------------|---------------------|------------------------|------------------|-----------------------|-------------------------------------|
| | | | Dose Escalation | 1 mg Dose | | | | Last Dose +30 ±3 days | Last Dose +90 ±10 days ^r |
| | | | Visit I1 | Visit I2 | Visit I3 | Visit I4 | | | |
| | | | Day 1 ^{a,b} | Week 4 ^b | Week 8 ^b | Week 12 ^{b,c} | | | |
| | Day 1 | Day 28±3 | Day 56±3 | Day 84±3 | | | | | |
| | ██████████ ██████████ | X | | | X | X | X | | |
| | Enterocutaneous and perianal fistula drainage ^k | X | | | | X | X | | |
| PK and PD Assessments | ██████████ ██████████ | | X | X | X | X | | | |

- ⁱ Week 12 colonoscopy should be performed either on day of visit or no more than 7 days prior to the visit date.
- ^j Colonoscopy does not need to be performed at the Early Term visit if one was completed within 8 weeks of the Early Term visit.
- ^k Enterocutaneous and perianal fistula drainage assessment will only be performed on patients with fistulas at baseline.
- ^l Blood samples for PK evaluation are to be taken up to 15-30 minutes prior to investigational drug administration (pre-dose) and just prior to discharge from the clinic (6-8 hours post-dose) on Day 1. Blood samples at subsequent visits will be trough level, taken just prior to investigational drug administration. The actual time of investigational drug administration for all visits with PK evaluation will be recorded. The blood sample at the 30-day and 90-day Safety Follow-Up Visit can be collected at any point during the visit. An additional PK sample will be obtained for patients with any AE resulting in discontinuation or SAE.
- ^m Week 12 flow cytometry analysis will only be performed for patients with a baseline sample (Day 1).
- ⁿ Prior to first dose of investigational drug, a 12-lead ECG will be performed. After the dose, patients will have hourly vital signs recorded at 1, 2, 3, 4, 5, and 6 hours post-dose. A second 12-lead ECG will be performed at the end of the observation period.
- ^o For females of childbearing potential only, serum beta hCG is required at screening and a urine beta hCG is required at each visit. Between scheduled visits up until the 90-day Safety Follow-up Visit, monthly urine pregnancy tests should be performed by the patient. If a urine pregnancy test result is positive, the investigator will instruct the patient to suspend further RPC1063 dosing, if applicable, and schedule a follow-up appointment as soon as possible. A serum pregnancy test will be performed for confirmation, including after the 90-day Safety Follow-up Visit, if needed. Counseling about pregnancy precautions and the potential risks of fetal exposure must be conducted for female subjects of childbearing potential. The Investigator will educate all FCBP about the different options of contraceptive methods or abstinence as appropriate. The subject will be re-educated every time her contraceptive measures/methods or ability to become pregnant changes. The female subject's chosen form of contraception must be effective by the time the female subject is randomized into the study (for example, hormonal contraception should be initiated at least 28 days before randomization).
- ^p The screening physical examination (PE) includes height and weight, other visits include weight. A complete PE will be performed at Screening and end of trial visit (Week 12 or Early Term). The complete PE will include a full examination of the skin for lesions as well as a check for visual symptoms (i.e., blurred vision or decreased visual acuity). An interim PE may be performed at all other visits. The interim PE will include areas with previously-noted abnormalities and those associated with any new complaints from the patient. The interim PE will also include a check for visual symptoms (i.e., blurred vision or decreased visual acuity).
- ^q DLCO, if locally available, will be done at Screening and Early Term.
- ^r The 90-day Safety Follow-up Visit should be conducted as a clinic visit. However, if the patient is not available for a clinic visit, a telephone call follow-up should be performed (with at least 3 attempts within the visit window) to record the pregnancy test result, concomitant medications, and AEs, including information regarding relationship of AEs to RPC1063.
- ^s If ALC is confirmed < 200 cells/μL, the Investigator will temporarily discontinue investigational drug. Laboratory testing will be repeated weekly until ALC is > 500 cells/μL. For patients whose ALC level is confirmed < 200 cells/μL and has not reached the acceptable range (ALC > 500 cells/μL) during the study, laboratory testing will be repeated at the 90-day Safety Follow-up Visit.

Abbreviations: AE = adverse event; ALC = absolute lymphocyte count; CDAI = Crohn's Disease Activity Index; DLCO = diffusion capacity of the lung for carbon monoxide; Early Term = Early Termination; ECG = electrocardiogram; PD = pharmacodynamic; PK = pharmacokinetic; SES-CD = Simple Endoscopic Score for Crohn's disease; TB = tuberculosis; WOCBP = women of child-bearing potential

Table 3: Schedule of Events for Extension Period

| | Trial Procedures | Extension Period | | | | | | | | | | | | | | | | | | | | | | | | | |
|--|---|------------------|-----------------|-----------------|-----------------|-----------------|-----------------|-----------------|------------|------------|------------|-------------|------------------|-------------------|-----------------------|-------------------------------------|------------------|---|------|------|------|------|------|------|-------|-------|-------|
| | | Treatment | | | | | | | | | | | | | | Early Term | Safety Follow-up | | | | | | | | | | |
| E1 ^{a,b} | E2 ^b | E3 ^b | E4 ^b | E5 ^b | E6 ^b | E7 ^b | E8 ^b | E9 ^b | E10 | E11 | E12 | E13 | E14 ^b | W12 | W 24 | | | | W 36 | W 48 | W 52 | W 64 | W 76 | W 88 | W 100 | W 112 | W 124 |
| Day 84 ±3 | Day 168 ±7 | Day 252 ±7 | Day 336 ±3 | Day 364 ±3 | Day 448 ±7 | Day 532 ±7 | Day 616 ±7 | Day 700 ±7 | Day 784 ±7 | Day 868 ±7 | Day 952 ±7 | Day 1036 ±7 | Day 1120 ±7 | Day of Early Term | Last dose +30 ±3 days | Last dose +90 ±10 days ^j | | | | | | | | | | | |
| Efficacy Assessments | Dispense investigational drug | | X | X | X | X | X | X | X | X | X | X | X | X | X | X | X ^k | | | | | | | | | | |
| | Administer investigational drug at clinic | | X | X | X | X | X | X | X | X | X | X | X | X | X | X | X | | | | | | | | | | |
| | Review drug compliance | | X | X | X | X | X | X | X | X | X | X | X | X | X | X | X | X | | | | | | | | | |
| | Concomitant medications | | X | X | X | X | X | X | X | X | X | X | X | X | X | X | X | X | X | X | | | | | | | |
| | CDAI patient diary | | X | X | X | X | X | X | X | X | X | X | X | X | X | X | X | X | X | | | | | | | | |
| | CDAI clinical score | | X | X | X | X | X | X | X | X | X | X | X | X | X | X | X | X | X | | | | | | | | |
| | Colonoscopy | | | | | X ^c | | | | | | | | | | | X ^d | | | | | | | | | | |
| SES-CD score | | | | | X | | | | | | | | | | | X ^d | | | | | | | | | | | |
| Colonic biopsy | | | | | X | | | | | | | | | | | X ^d | | | | | | | | | | | |
| ██████████ ██████████ ██████████ | | X | | | X | | | | | | | | | | | X | X | | | | | | | | | | |

| | Trial Procedures | Extension Period | | | | | | | | | | | | | | | | |
|--------------------------------------|--|-------------------|-----------------|-----------------|-----------------|-----------------|-----------------|-----------------|-----------------|-----------------|------------|-------------|-------------|-------------------|-----------------------|-------------------------------------|------------------|---|
| | | Treatment | | | | | | | | | | | | | | Early Term | Safety Follow-up | |
| | | E1 ^{a,b} | E2 ^b | E3 ^b | E4 ^b | E5 ^b | E6 ^b | E7 ^b | E8 ^b | E9 ^b | E10 | E11 | E12 | E13 | E14 ^b | | | |
| | | W12 | W 24 | W 36 | W 48 | W 52 | W 64 | W 76 | W 88 | W 100 | W 112 | W 124 | W 136 | W 148 | W 160 | | | |
| Day 84 ±3 | Day 168 ±7 | Day 252 ±7 | Day 336 ±3 | Day 364 ±3 | Day 448 ±7 | Day 532 ±7 | Day 616 ±7 | Day 700 ±7 | Day 784 ±7 | Day 868 ±7 | Day 952 ±7 | Day 1036 ±7 | Day 1120 ±7 | Day of Early Term | Last dose +30 ±3 days | Last dose +90 ±10 days ^j | | |
| | Enterocutaneous and perianal fistula drainage ^e | | X | | | X | | | | | | | | | X | X | | |
| PK and PD Assessments | ██████████ | | X | | | X | | | | | | | | | X | X | X | |
| | ██████████ | | X | | | X | | | | | | | | | X | X | X | X |
| Safety Assessments | PK blood sampling ^f | | X | | | X | | | | | | | | | X | X | X | X |
| | Adverse events | | X | X | X | X | X | X | X | X | X | X | X | X | X | X | X | X |
| | 12-Lead ECG | | | | | X | | | | | | | | | | X | | |
| | Vital signs | | X | X | X | X | X | X | X | X | X | X | X | X | X | X | X | |
| | Hematology ^l | | X | X | X | X | | X | | X | | X | | X | | X | X | |
| | Blood chemistry | | X | X | X | X | | X | | X | | X | | X | | X | X | |
| | Urine pregnancy test ^g | | X | X | X | X | X | X | X | X | X | X | X | X | X | X | X | X |
| | Urinalysis | | | X | | X | | X | | X | | X | | X | | X | | |
| Physical Examination ^h | | X | X | X | X | X | X | X | X | X | X | X | X | X | X | X | | |
| Pulmonary function test ⁱ | | X | | | X | | | | | X | | | | X | X | | | |

| | Trial Procedures | Extension Period | | | | | | | | | | | | | | Early Term | Safety Follow-up | |
|--|------------------------------|-------------------|-----------------|-----------------|-----------------|-----------------|-----------------|-----------------|-----------------|-----------------|------------|------------|------------|-------------|------------------|-------------------|-----------------------|-------------------------------------|
| | | Treatment | | | | | | | | | | | | | | | | |
| | | E1 ^{a,b} | E2 ^b | E3 ^b | E4 ^b | E5 ^b | E6 ^b | E7 ^b | E8 ^b | E9 ^b | E10 | E11 | E12 | E13 | E14 ^b | | | |
| | | W12 | W 24 | W 36 | W 48 | W 52 | W 64 | W 76 | W 88 | W 100 | W 112 | W 124 | W 136 | W 148 | W 160 | | | |
| | | Day 84 ±3 | Day 168 ±7 | Day 252 ±7 | Day 336 ±3 | Day 364 ±3 | Day 448 ±7 | Day 532 ±7 | Day 616 ±7 | Day 700 ±7 | Day 784 ±7 | Day 868 ±7 | Day 952 ±7 | Day 1036 ±7 | Day 1120 ±7 | Day of Early Term | Last dose +30 ±3 days | Last dose +90 ±10 days ^j |
| | Optical coherence tomography | | | | | X | | | | | X | | | | X | X | | |

- ^a The duration of Visit E1 will be approximately 3 hours.
- ^b Trial visits should be scheduled in the morning, when possible. At trial Visits Week 24, 52 and at Week 160, patients should be instructed to withhold the dose until the trial visit and the dose should be administered during the visit.
- ^c At Week 52, a colonoscopy should be performed either on the day of visit or no more than 7 days prior to the visit date.
- ^d Colonoscopy, biopsy, and SES-CD score do not need to be performed at the Early Term visit if the Early Term Visit occurs within 8 weeks of the Week 12 colonoscopy or after the Week 52 colonoscopy assessment.
- ^e Enterocutaneous and perianal fistula drainage assessment will only be performed on patients with fistulas at baseline.
- ^f Blood samples at each visit will be trough level, taken just prior to investigational drug administration. The actual time of investigational drug administration for all visits with PK evaluation will be recorded. The blood sample at the Follow-up visit can be collected at any point during the visit. An additional PK sample will be obtained for patients with any AE resulting in discontinuation or SAE.
- ^g For females of childbearing potential only, serum beta hCG is required at screening and a urine beta hCG is required at each visit. Between scheduled visits up until the 90-day Safety Follow-up Visit, monthly urine pregnancy tests should be performed by the patient. If a urine pregnancy test result is positive, the investigator will instruct the patient to suspend further RPC1063 dosing, if applicable, and schedule a follow-up appointment as soon as possible. A serum pregnancy test will be performed for confirmation, including after the 90-day Safety Follow-up Visit, if needed. Counseling about pregnancy precautions and the potential risks of fetal exposure must be conducted for female subjects of childbearing potential. The Investigator will educate all FCBP about the different options of contraceptive methods or abstinence as appropriate. The subject will be re-educated every time her contraceptive measures/methods or ability to become pregnant changes. The female subject’s chosen form of contraception must be effective by the time the female subject is randomized into the study (for example, hormonal contraception should be initiated at least 28 days before randomization).
- ^h A complete PE will be performed at Week 160 or Early Term, whichever is applicable. The complete PE will include a full examination of the skin for lesions as well as a check for visual symptoms (i.e., blurred vision or decreased visual acuity). An interim physical examination may be performed at all other visits; weight will be recorded at all visits. The interim PE will include areas with previously-noted abnormalities and those associated with any new complaints from the patient. The interim PE will also include a check for visual symptoms (i.e., blurred vision or decreased visual acuity).
- ⁱ DLCO, if locally available, will be done at Week 52 and Early Term.
- ^j The 90-day Safety Follow-up Visit should be conducted as a clinic visit. However, if the patient is not available for a clinic visit, a telephone call follow-up should be performed (with at least 3 attempts within the visit window) to record the pregnancy test result, concomitant medications, and AEs, including information regarding relationship of AEs to RPC1063.

^k For eligible patients who are entering the Phase 3 open-label extension CD Study RPC01-3204 at a future date (not on visit Week 160), investigational drug will be dispensed in this study. For eligible patients who are immediately entering the Phase 3 open label extension CD Study RPC01-3204 on the same day as visit Week 160, investigational drug will be dispensed in Study RPC01-3204.

^l If ALC is confirmed < 200 cells/ μ L, the Investigator will temporarily discontinue investigational drug. Laboratory testing will be repeated weekly until ALC is > 500 cells/ μ L. For patients whose ALC level is confirmed < 200 cells/ μ L and has not reached the acceptable range (ALC > 500 cells/ μ L) during the study, laboratory testing will be repeated at the 90-day Safety Follow-up Visit.

Abbreviations: AE = adverse event; ALC = absolute lymphocyte count; CD = Crohn's disease; CDAI = Crohn's Disease Activity Index; DLCO = diffusion capacity of the lung for carbon monoxide; Early Term = Early Termination; ECG = electrocardiogram; PK = pharmacokinetic; PD = pharmacodynamic; SES-CD = Simple Endoscopic Score for Crohn's disease

